responses such as vasodilation and chemotaxis of leukocytes to sites of inflammation. Since rhinovirus appears to have a different pathophysiology of immune response, it is possible that bronchiolitis secondary to other non-RSV viruses may respond to different immunomodulators, specifically steroids. This pilot study will contribute knowledge about the utility of steroid use in non-RSV bronchiolitis both clinically in terms of patient outcomes, and economically in terms of hospital utilization. If the proposed aims are achieved, this contribution will be significant because there may be reason to re-evaluate the current AAP Guidelines for diagnosis and management of bronchiolitis. We hypothesize that steroid use in this cohort will reduce length of stay, and subsequently reduce hospital costs through reduction of both 7-day same cause readmission rate and escalation of care (transfer to ICU).

In the short term, our work will address the feasibility of conducting a clinical trial assessing the utility and safety of steroid use in non-RSV bronchiolitis in the inpatient setting. Moreover, the work proposed here will develop a platform for a larger, multi-center double-blinded randomized control trial addressing the same question. This pilot study will establish expected target enrollment rates, adherence and drop-out rates, expected length of stay, and expected severity of disease assessed with the Kristjansson score at time of discharge for use in sample size and power calculations for future phase II/III trials. Thus, this work will be a foundational resource providing a research strategy and protocol for a larger scale trial.

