Objectives: The long-term objective of this research is to improve the clinical course and outcomes of children diagnosed with non-RSV bronchiolitis. The objective of this proposal is to determine the efficacy of steroid use as a treatment modality in children < 24 months diagnosed with non-RSV bronchiolitis. The central hypothesis is that the use of standard airway- dose steroids (0.6mg/kg dexamethasone) will improve the clinical outcome of children hospitalized for non-RSV bronchiolitis, which will be evident by decreased length of stay. The central hypothesis was formulated based on data showing an interleukin response to rhinovirus that is dampened by steroid administration. The rationale underlying this proposal is that the completion of this research will identify a new treatment option for non-RSV bronchiolitis. The central hypothesis work may change the currently accepted practice guidelines for diagnosis and management of bronchiolitis. The central hypothesis will be tested by pursuing these specific aims:

1) To determine the extent to which steroid administration reduces hospital length of stay for clinical non-RSV bronchiolitis.

Hypothesis: Steroid administration will decrease duration of admission from time of admission from the emergency department (ED) to time of discharge instructions being printed.

2) To determine the extent to which steroid administration reduces the severity of bronchiolitis by using the Modified Tal Score to assess patients at admission, enrollment (if differs from admission time), 24 hours after administration of intervention, and discharge.

Hypothesis: Steroid administration will reduce the severity of bronchiolitis, which will be evident by a lower Modified Tal Score at 24 hours after medication administration.

Design/Methods: The study is a double-blind, randomized control trial. All participants will be treated with standard of care for viral bronchiolitis, including supportive care. All participants will also have had some form of viral testing confirming they do not have RSV or influenza. In

addition, half the participants will receive standard airway dosing of dexamethasone (0.6mg/kg) orally, and the other half will received placebo (sugar water 0.6mL/kg).

Eligibility Criteria:

Inclusion criteria:

- 1. Less than or equal to 24 months
- 2. First episode of wheezing or a clinical diagnosis of bronchiolitis
- 3. Admitted to the general pediatric service at UPMC Children's Hospital of Pittsburgh

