Statistical Considerations: We will compare mean duration of hospital stay in the two treatment groups using the student T-test. As a secondary outcome we will compare mean scores on the Kristjansson scale (range 0 to 9) at each time point using generalized estimating equations

between the two treatment groups. Because this is a pilot study we will be underpowered, however, this study will provide data that will allow us to estimate the sample size needed for a future study. The number of time points to be used for the generalized estimating equation can be determined ad hoc to include a reasonably balanced sample to make the comparison valid.

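### The GEE for severity names no small-sample correction and ignores the pre-dose score: in a small pilot its p-values and intervals may be too optimistic, and precision is lost

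*Combined protocol and SAP*

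**What the plan says.** Statistical Considerations gives the secondary analysis in one sentence: "we will compare mean scores on the Kristjansson scale (range 0 to 9) at each time point using generalized estimating equations". It then states "Because this is a pilot study we will be underpowered" and adds that "The number of time points to be used for the generalized estimating equation can be determined ad hoc".

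Aim 2, under Objectives, plans to "assess patients at admission, enrollment (if differs from admission time), 24 hours after administration of intervention, and discharge". Its hypothesis is a lower score 24 hours after medication. One or two of the four assessments therefore fall before dosing, and the contrast of interest falls after it.

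The document states no sample size, significance level, working correlation, variance estimator, reference distribution, small-sample correction or covariate for this analysis. Aim 2 names the Modified Tal Score, while Statistical Considerations names the Kristjansson scale.

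**The concern.** The usual GEE variance is the robust (sandwich) estimator, referred to a normal distribution. Both parts rely on a large number of children. With few children the sandwich estimator is biased low, and the normal reference ignores the fact that the variance is itself estimated. Both errors make p-values too small and intervals too narrow. A plan that says only GEE leaves that analysis open.

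The second issue does not depend on the variance estimator. Means are to be compared at each time point, and some time points precede the dose. A contrast there cannot show a treatment effect. The score measured then is useful as a covariate for the later scores, but the plan gives it no such role, so a small trial gives up precision that it has already paid to collect.

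At stake is the secondary efficacy comparison at 24 hours: how often a difference is declared when there is none, and how precisely it is estimated.

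**Working it through.** The plan has no figure of its own to reproduce.

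**Inputs from the document.** Allocation is 1:1 (Design/Methods: "half the participants will receive standard airway dosing of dexamethasone (0.6mg/kg) orally"). Means are compared separately "at each time point using generalized estimating equations".

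**Assumed, because not stated.** Two-sided 5% level; n = 10 to 50 children per arm; uncorrected sandwich variance with a normal reference; normal, complete data for the closed forms.

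**1. False-positive rate and interval width.** With a separate mean for each arm and time point, the sandwich variance of the arm difference uses divisor n where the unbiased variance uses n − 1. The Wald statistic is therefore t × √(n/(n − 1)), with t on 2n − 2 degrees of freedom.

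- Cut-off on the t scale: c = 1.96 × √((n − 1)/n)
- Type I error = P(|t| > c), with 2n − 2 degrees of freedom
- Interval width relative to the correct t interval = c / t(0.975; 2n − 2)

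| n per arm | c | t(0.975) | Type I error | Relative width |
|---|---|---|---|---|
| 10 | 1.859 | 2.101 | 7.9% | 0.885 |
| 15 | 1.893 | 2.048 | 6.9% | 0.924 |
| 20 | 1.910 | 2.024 | 6.4% | 0.944 |
| 30 | 1.927 | 2.002 | 5.9% | 0.963 |
| 50 | 1.940 | 1.984 | 5.5% | 0.978 |

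At 100 per arm the error is 5.3%.

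**2. Check by simulation.** Assumptions: no effect, four time points, integer scores limited to 0-9, SD 1.8, within-child correlation 0.5, exchangeable working correlation, and 0% or 30% of 24-hour scores missing unrelated to outcome. About 2,000 trials were run per setting (Monte Carlo error about 0.5 percentage points).

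| n per arm | Uncorrected, normal reference (0% / 30% missing) | Mancl-DeRouen, t reference (0% / 30% missing) |
|---|---|---|
| 10 | 7.3% / 9.1% | 3.4% / 4.4% |
| 15 | 7.2% / 6.8% | 5.1% / 3.8% |
| 20 | 6.4% / 7.0% | 4.1% / 4.8% |
| 30 | 5.6% / not run | 4.6% / not run |

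The correction removes the inflation and is a little conservative at the smallest size.

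**3. Value of the pre-dose score.** For correlation r between the pre-dose and 24-hour scores, the variance of the adjusted difference relative to the unadjusted one is (1 − r²) × (2n − 3)/(2n − 4). The second factor is the cost of estimating the slope: 17/16 = 1.0625 at n = 10 and 57/56 = 1.018 at n = 30.

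| r (assumed) | Variance cut, n = 10 | Variance cut, n = 30 |
|---|---|---|
| 0.3 | 1 − 0.91 × 1.0625 = 3% | 1 − 0.91 × 1.018 = 7% |
| 0.5 | 1 − 0.75 × 1.0625 = 20% | 1 − 0.75 × 1.018 = 24% |
| 0.7 | 1 − 0.51 × 1.0625 = 46% | 1 − 0.51 × 1.018 = 48% |

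**4. Does adjustment pay for the correction?** Bringing the uncorrected interval to its correct width lengthens it by 1/0.885 = 1.13 at 10 per arm and 1/0.963 = 1.04 at 30. Adjustment offsets this when (1 − r²) × (2n − 3)/(2n − 4) is at most the squared relative width. At n = 10, 1 − r² = 0.885²/1.0625 = 0.737, so r is about 0.51. At n = 30, 1 − r² = 0.963²/1.018 = 0.911, so r is about 0.30.

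**The case against.** The strongest reply is that the plan never says it will use uncorrected robust errors. That stands. A reader might infer that the planned analysis has a false-positive rate above 5%. The document does not support this, because it neither specifies nor excludes a correction and gives no sample size or level. Nor does the word underpowered fix a small number: at 50 per arm the error is 5.5% and at 100 it is 5.3%, which hardly matters.

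Two further inferences should be resisted. Joint tests over several time points would be inflated more, but the plan describes comparisons at each time point and aim 2 turns on 24 hours alone, so no joint-test figure applies. It is also tempting to say that the narrow intervals would mislead the next trial's planning. The plan mentions no confidence interval. What the closing paragraph of the background carries forward is enrolment, adherence and drop-out rates, expected length of stay and severity at discharge, not the 24-hour arm difference.

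On the pre-dose score, leaving it out does not bias a randomised comparison, and the gain depends on a correlation that the document does not give. Both are true. The loss is one of precision, and it may be small.

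Finally, this is a secondary outcome in a pilot, and the open choice of time points and the two named scales are arguably more urgent. That limits the priority of this point but does not answer it: the plan is where the variance estimator and covariate should be fixed before data are seen.

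**Conclusion.** The concern holds as a conditional one. The plan commits to a large-sample method in a self-described pilot without a safeguard. If uncorrected errors with a normal reference are used at a two-sided 5% level, the 24-hour contrast has a false-positive rate that is material at 10 to 15 per arm (7.9% to 6.9%), modest at 20 to 30 (6.4% to 5.9%) and negligible from about 50 (5.5%). These figures rest on assumed arm sizes; the closed forms also assume normal, complete data.

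The missing role for the pre-dose score does not depend on the unstated variance estimator. Contrasts at pre-dose visits say nothing about treatment. Adjustment would lower the variance of the 24-hour difference by 3% to 48% over assumed correlations of 0.3 to 0.7 at 10 to 30 per arm.

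This should be changed because the remedy is cheap, not because the planned analysis has been shown to be invalid.

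**What to change.** Reconcile Objectives (aim 2) and Statistical Considerations on which severity scale is used. Keep the GEE and that scale, and add:

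*Post-dose scores (24 hours after dosing and discharge) are the outcomes, with the last pre-dose score (enrolment, or admission if no separate enrolment score exists) as a covariate; the arm difference at 24 hours is the main contrast. Mancl-DeRouen corrected standard errors with a t reference (number of children minus the number of child-level parameters) will be used.*

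The sentence that leaves the number of time points open must be amended to match. The sample size, significance level and working correlation should be stated alongside.

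**Cost.** A few lines of text and standard software options; no new data. Reaching the correct width makes intervals about 4% (30 per arm) to 13% (10 per arm) wider than uncorrected ones. Mancl-DeRouen overshoots slightly. With complete data and before covariate adjustment it multiplies the correct width by √(n/(n − 1)), so the total is 1.04 × 1.017, about 6%, at 30 per arm and 1.13 × 1.054, about 19%, at 10. This is why it is slightly conservative at the smallest sizes. Baseline adjustment recovers the 4-13% only if the correlation is moderate (about 0.5 or more at 10 per arm, about 0.3 at 30). Recovering the overshoot as well needs somewhat more.

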- 4. Between 2/1/20 and 12/31/22
- 5. Ability of a parent or guardian to understand and comply with the study procedures
- 6. Signed written informed consent by parent or guardian
- 7. Respiratory viral testing obtained within 24 hours of admission

Exclusion Criteria

1. Preterm birth < 35 weeks

- 2. Presence of underlying cardiopulmonary, neuromuscular, or other complex disease
- 3. Admission to the PICU

4. Coinfection with influenza infection, RSV, acute COVID-19, or concomitant bacterial infection (such as pneumonia) as documented within the past 72 hours (per chart review)

5. History of allergy or reaction to steroids

6. History of an underlying chronic medical condition -including chronic heart disease, chronic lung disease (except asthma),congenital anomalies of the airways or lung, cystic fibrosis, chronic renal disease including nephrotic syndrome, protein losing enteropathy of any cause, severe malnutrition, glaucoma, neurocognitive disorders, metabolic disorders (including phenylketonuria, diabetes mellitus), or genetic disorders (note: genetic syndromes such as Down syndrome and Edwards Syndrome are excluded; however, children with genetic disorders (e.g., hemophilia) but who do not have a genetic syndrome may not satisfy this particular exclusion criterion; it is important that children with such genetic disorders do not have symptoms and/or comorbidities that would pose additional risk to them nor jeopardize the adequacy of study assessments.")

7. History of a condition that compromises the immune system -HIV infection, primary immunodeficiency, anatomic or functional asplenia; receipt of a hematopoietic stem cell or solid organ transplant at any time; receipt of immunosuppressive therapy including chemotherapeutic agents, biologic agents, antimetabolites or radiation therapy during the past 12 months; or daily use of systemic corticosteroids for more than 7 consecutive days during the past 14 days. 8. Any other condition that in the judgment of the investigator precludes participation because it could affect the safety of the subject

9. Any patient admitted to the inpatient general pediatrics teams from 4pm-9pm, as patients are to be enrolled in the study within 10 hours of admission and medication distribution cannot be complete until 7am.

10. Any patient who has previously received a dose of steroids medication in the emergency department within 24 hours prior to admission

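### Aim 2 hypothesises a difference on the Modified Tal Score at 24 hours, but the only planned severity analysis is on the Kristjansson scale, with time points left open

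*Combined protocol and SAP*

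**What the plan says.** Three sections of the combined protocol and SAP deal with severity.

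- **Objectives, specific aim 2.** The aim is to find how far steroid treatment "reduces the severity of bronchiolitis by using the Modified Tal Score to assess patients at admission, enrollment (if differs from admission time"), and then "24 hours after administration of intervention, and discharge". Its hypothesis is a reduction in severity, "which will be evident by a lower Modified Tal Score at 24 hours after medication administration".
- **Statistical Considerations.** For the secondary outcome the plan will "compare mean scores on the Kristjansson scale (range 0 to 9) at each time point", by GEE, between the two treatment groups. It adds: "The number of time points to be used for the generalized estimating equation can be determined ad hoc", the purpose being "to include a reasonably balanced sample to make the comparison valid".
- **Scientific background, closing paragraph on the pilot's purpose.** Among the quantities the pilot is to supply is "expected severity of disease assessed with the Kristjansson score at time of discharge for use in sample size and power calculations" in later trials.

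**The concern.** An aim, its hypothesis and its analysis should concern the same measurement. Here the aim and hypothesis name one instrument and the analysis names another. An analyst who follows Statistical Considerations to the letter produces a Kristjansson comparison, which does not test the stated Aim 2 hypothesis. An analyst who follows Aim 2 has a hypothesis and an assessment schedule but no analysis for that score.

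If both scores were recorded, nothing says which is the secondary outcome, so the choice could be made after the results by treatment group are known. If only one was recorded, at least one section names an instrument that was not used. Either way the text needs correcting.

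The open number of time points adds to this. The hypothesis is specific to 24 hours, yet the analysis does not commit to keeping that time point. Neither the score nor the time of the Aim 2 comparison is therefore fixed.

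**Working it through.** The plan states no sample size, power or effect size for severity, so there is no figure to reproduce. The check is a comparison of every mention of a severity score.

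| Place | Role | Instrument | Range given | Time |
|---|---|---|---|---|
| Objectives, aim 2 | Aim | Modified Tal | none | admission, enrolment if different, 24 hours after intervention, discharge |
| Objectives, aim 2 hypothesis | Hypothesis | Modified Tal | none | 24 hours after medication |
| Statistical Considerations | Analysis (GEE) | Kristjansson | 0 to 9 | each time point, number ad hoc |
| Scientific background | Planning parameter | Kristjansson | none | discharge |

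1. **Counts.** Modified Tal is named 2 times, both under aim 2. Kristjansson is named 2 times, once in the background and once in the analysis. Sections naming both: 0.
2. **Links.** No sentence says that the two are the same instrument, that one converts to the other, or that both are collected. All four mentions stand in complete, legible sentences, so neither redaction nor broken text accounts for the difference.
3. **Hypothesis to analysis.** The hypothesis needs a between-group comparison of Modified Tal at 24 hours. The analysis supplies a between-group comparison of Kristjansson at time points still to be chosen. Read literally, the first has no analysis and the second has no aim.
4. **Time points.** Aim 2 lists up to four assessments. One of them, enrolment, exists only for children whose enrolment time differs from admission, so some imbalance is built into the schedule and a balance rule has an evident use there. But the rule covers the number of time points generally. It does not exempt the 24-hour assessment, and the plan does not define what counts as reasonably balanced.
5. **Reach.** Length of stay is compared by a t-test that uses neither score, so nothing here alters that analysis.

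**The case against.** The strongest reply is that this is a labelling inconsistency in a secondary outcome of a pilot that says openly it is underpowered. The central hypothesis is judged on length of stay. Statistical Considerations does name a scale, a range, a method and the groups, and its time-point rule rests on balance, not on results. The background cites a mean stay of 3.3 days for bronchiolitis (a 2002 estimate), so many children would plausibly still be in hospital at 24 hours, and that assessment is not an obvious one to drop.

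Most of this stands, and it limits the weight of the point. It does not remove it: low power does not excuse leaving the measured quantity unidentified, and a time point that is unlikely to be dropped is still not protected.

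Four stronger readings are tempting, and the documents support none of them.

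- **The severity analysis cannot be run.** It can: a Kristjansson GEE is runnable as described. What is missing is an analysis of the score that the hypothesis names.
- **A planner of the future trial could not tell which scale the severity figures belong to.** On the planning parameter the text is consistent: the background and the analysis section both name Kristjansson. The conflict lies between the aim and the analysis.
- **One name is a leftover from a change of instrument, or the range of 0 to 9 is wrong.** No change of instrument is recorded, and the range is attached only to Kristjansson. Collection of both scores is not excluded. Nor can it be concluded that Kristjansson was scored only at discharge, because the analysis compares it at each time point.
- **The instrument must already have been settled in practice**, because the document is dated 11/9/2022 and the admission window is "Between 2/1/20 and 12/31/22". Those dates show calendar time only. The documents do not say when enrolment began, how many children were enrolled or what was scored.

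**Conclusion.** The mismatch is real and is wrong as written, not merely under-described. Followed literally, the plan evaluates severity on a different instrument from the one Aim 2 hypothesises about, and it does not guarantee the 24-hour comparison. It touches one of the two specific aims, but only as the secondary outcome of a pilot. It should be corrected, and it is not a critical defect of the trial.

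The conclusion rests on the text alone. It assumes nothing about which instrument was used, whether the two scores share items or a range, how many children have been enrolled, or the state of blinding. Which section is in error cannot be decided from the documents; only the study records can settle that.

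**What to change.** Before any comparison of severity by treatment group:

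1. Reconcile the Scientific background, aim 2 with its hypothesis, and Statistical Considerations to the instrument actually recorded at the Aim 2 time points, and give its range. If both were recorded, state which one is the secondary outcome.
2. In Statistical Considerations, state that the 24-hour between-group contrast on that instrument is always estimated from the GEE, and that the balance criterion applies only to the other time points.
3. If that instrument was not recorded at 24 hours, say so and report that the Aim 2 hypothesis cannot be tested as stated.

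The cost is a few wording changes, plus less freedom to drop the 24-hour time point if the data there turn out unbalanced. Wording cannot supply 24-hour scores that were never recorded, which is why the third step is disclosure.

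### The analysis section does not designate Aim 2's 24-hour severity comparison and lets the GEE time points be settled ad hoc, with no rule for children discharged before 24 hours

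*Combined protocol and SAP*

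**What the plan says.** All references are to the combined protocol and SAP.

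- **Objectives, Aim 2.** The hypothesis is tied to one time: a "lower Modified Tal Score at 24 hours after medication administration". The scale is to be used "to assess patients at admission, enrollment (if differs from admission time), 24 hours after administration of intervention, and discharge". That gives up to two pre-dose scores, the enrollment one being conditional, and two post-dose scores.
- **Objectives, Aim 1.** "Steroid administration will decrease duration of admission from time of admission from the emergency department (ED) to time of discharge instructions being printed".
- **Design/Methods.** "The study is a double-blind, randomized control trial".
- **Statistical Considerations.** The secondary analysis compares "mean scores on the Kristjansson scale (range 0 to 9) at each time point using generalized estimating equations". It mentions neither 24 hours nor Aim 2. It closes with: "The number of time points to be used for the generalized estimating equation can be determined ad hoc to include a reasonably balanced sample".
- **Scientific background.** Among the planning inputs the pilot is to supply is "expected severity of disease assessed with the Kristjansson score at time of discharge".

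The documents give no sample size, significance level, score SD or discharge criteria.

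**The concern.** The aim names one comparison and the analysis section designates none. What it adds is a permission: the number of visits in the model may be "determined ad hoc to include a reasonably balanced sample to make the comparison valid". Nothing says how balanced is balanced enough, whether 24 hours must stay in, or when the choice is made. The reported severity result could therefore be something other than the contrast Aim 2 predicts.

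The stated justification also falls short. A 24-hour score exists only for children still in hospital at that time. Who those children are depends on length of stay, which is the Aim 1 outcome and is expected to respond to treatment. Equal or near-complete numbers at a visit do not repair a comparison whose membership treatment may alter. The plan has no rule for the children who left earlier.

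At stake is the severity estimate that a larger trial would be planned on, not the primary length-of-stay comparison.

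**Working it through.** The plan gives no figure to reproduce. The numbers below are illustrations on stated assumptions.

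**1. The texts side by side.** Aim 2: one scale score, at 24 hours. Analysis: scores at all time points, no key contrast, number of time points open. Taken alone, the comparison at all time points includes 24 hours. The closing sentence then allows visits to be left out, and it applies to the 24-hour visit as much as to the conditional enrollment score.

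**2. Share of children without a 24-hour score.** Inputs:
- mean stay 3.3 days = 79.2 h (Scientific background, a general 2002 figure);
- gamma-distributed stay with CV 0.6 to 1.0 (assumed);
- dose at d = 0 or 10 h after admission (exclusion criterion 9 has enrollment within 10 hours; dosing at enrollment is assumed).

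With shape 1/CV² and scale 79.2 × CV², the share gone within 24 h of the dose, among children in hospital at the dose, is [F(d+24) − F(d)] / [1 − F(d)].

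| CV | d = 0 h | d = 10 h |
|---|---|---|
| 0.6 | 0.074 | (0.1531 − 0.0092)/(1 − 0.0092) = 0.145 |
| 0.8 | 0.169 | 0.221 |
| 1.0 | 0.261 | 0.261 |

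So 7% to 26% lack the score, and 74% to 93% have it. With an assumed mean stay of 48 to 60 h instead, the missing share is 13% to 39%.

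**3. Bias if only children still in hospital are compared.** Suppose treatment does not change the 24-hour score but more treated children leave early. Suppose also that leavers are the least ill on a latent normal variable with correlation ρ to the score. If a share p has left, the mean of those remaining is raised by ρ·φ(z)/(1 − p) SD, where z is the p-quantile of the standard normal. The factor φ(z)/(1 − p) is 0.195 at p = 0.10, 0.274 at 0.15, 0.350 at 0.20 and 0.497 at 0.30. The steroid arm then looks worse by:
- 10% against 15% gone, ρ = 0.3: 0.3 × (0.274 − 0.195) = 0.02 SD;
- 10% against 20% gone, ρ = 0.5: 0.5 × (0.350 − 0.195) = 0.08 SD;
- 10% against 30% gone, ρ = 0.7: 0.7 × (0.497 − 0.195) = 0.21 SD.

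With equal shares gone, the shift is zero.

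**4. Type I error, assumed two-sided 0.05.**
- *Arm-blind choice for balance.* If treatment affects neither score nor stay, a choice of visits made from pooled data carries no information about allocation. The later test keeps its level.
- *24 hours and discharge both tested, neither designated.* The error is 1 − P(|Z₁| < 1.96 and |Z₂| < 1.96). Independent scores give 1 − 0.95² = 0.0975. Correlations 0.3, 0.5 and 0.7 give 0.095, 0.091 and 0.084. Simulated t-tests with 10 to 30 per arm gave 0.082 to 0.097.
- *One fixed 24-hour test* in the same simulations: 0.048 to 0.052.

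**The case against.** Much of the case on the other side stands.

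- **The 24-hour visit is already in.** Protocol and SAP are one document, Aim 2 states the contrast, and a comparison at all time points covers it. True: the visit is not excluded. What remains is that it is not designated and may be dropped.
- **The criterion is balance and the trial is blinded.** Also true. A reader might infer that the rule steers towards dropping the 24-hour visit. The documents do not show that. The conditional enrollment score is at least as natural a target, availability of 74% to 93% could well count as balanced, and no threshold is set.
- **False positives.** A reader might infer that the ad hoc sentence inflates type I error. Chosen blind to arm, it does not. The 8% to 10% is ordinary multiplicity from two undesignated visits. Picking the most favourable set with results in view would be a different matter, but the plan does not describe that.
- **A hidden effect at discharge.** A reader might infer that, with 24 hours dropped, the discharge score would conceal most of a real effect. That needs discharge to be triggered by severity, and the documents give no discharge criteria. Faster recovery would in that case still show in length of stay.
- **It is a secondary outcome in a pilot that declares itself underpowered.** This lowers the weight of the point. It does not remove it, because the pilot exists to supply planning estimates and naming a contrast needs no extra children.

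**Conclusion.** The concern holds in a limited form. The analysis section does not designate the comparison that Aim 2 states. It allows the visits in the GEE to be settled ad hoc, with no threshold, no protection for 24 hours and no timing relative to unblinding, and it is silent on children who leave before 24 hours.

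The missing share is about 7% to 26% under the assumed stay distribution and dosing times. The possible bias against treatment, about 0.02 to 0.21 SD in the cases worked, rests on an assumed difference between arms in early discharge and an assumed link between severity and leaving. It is zero if equal shares leave. Under arm-blind choice, type I error is a concern only if 24 hours and discharge are both tested with neither named.

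The documents do not support saying that the 24-hour visit will be dropped, or that its results have been or would be selected. The aims and the analysis section also name different severity scales (Modified Tal and Kristjansson). That is a separate conflict, to be reconciled as its own point.

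**What to change.** Before unblinding, amend Statistical Considerations as follows.

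1. Replace the ad hoc sentence with a fixed set of visits.
2. Name the between-arm difference in the 24-hour post-dose score as the key severity comparison, adjusted for the last pre-dose score, with a 95% CI. ANCOVA would serve, as would a visit-specific contrast in the GEE with a small-sample correction. In simulation with 10 to 30 per arm, 24-hour ANCOVA held its level at 0.046 to 0.053.
3. State how children without a 24-hour score because of early discharge enter the comparison. One option is to carry the discharge score to 24 hours, with a sensitivity analysis that ranks early discharge as the best outcome (simulated level of that rank test 0.049 to 0.055, with 15% discharged early).
4. Report the discharge score as a secondary estimate with a CI, because the pilot needs it for planning.

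The cost is about one paragraph. No new assessments are needed, since the pre-dose, 24-hour and discharge scores are already scheduled. The downsides are that the freedom to choose visits later is lost, and that the early-discharge rule is itself an assumption, hence the sensitivity analysis.
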